2.4 Definition of outcome measures

2.4.1.1 Primary objectives/endpoints

	Objective	Outcome
Primary	To evaluate efficacy of CBZ for the treatment of children with MCDS who are ambulant but have not yet reached skeletal maturity (open epiphyses)	Alteration from baseline in growth velocity over 12 months
	To determine if the level of efficacy warrants a subsequent formal development programme for CBZ in this indication.	Growth velocity follow-up data at 12 months post treatment initiation

Participants undergo an observational phase (12-18 months for Stage 1 participants; 6 months for Stage 2 participants) prior to starting treatment. Measurements taken include data on height and weight. The same measurements are taken at various time points during the treatment period, allowing an assessment of growth velocity and any change which might be due to treatment.

2.4.1.2 Secondary objectives/endpoints

	Objective	Outcome		
Secondary	To evaluate the effect of CBZ on height in children with MCDS over 12 months	Alteration from baseline in height percentile over 12 months		
	To evaluate the effect of CBZ on bone conformation in children with MCDS over 12 months	Alteration from baseline in long bone alignment and configuration over 12 month as measured by X-ray analysis		
To evaluate the effect of CBZ on pain in children with MCDS over 12 monthsAlteration from over 12 months• PEDSQL Pa • PEDSQL Pa		 Alteration from baseline in pain perception over 12 months as measured by: PEDSQL Pain Coping Inventory PEDSQL Pain Questionnaire 		

To evaluate the effect of CBZ on health related quality of life of children with MCDS	Alteration from baseline in HRQOL scores over 12 months as measured by:		scores over			
over 12 months	•	Paediatric (PedsQL) EQ-5D-Y	Quality	of	Life	Inventory

2.4.1.2.1 Alteration from baseline in height percentile over 12 months

Total height (length if age <2 years); sitting height (age \ge 5 years) and crown-rump length (age <5 years) are recorded at each baseline and treatment visit.

Height for age and sex, *zscores* are calculated using the ZANTHRO function in STATA; the "British 1990 Growth Reference" charts are used as the standard.

Vidmar, S. I., Cole, T. J., & Pan, H. (2013). Standardizing Anthropometric Measures in Children and Adolescents with Functions for Egen: Update. The Stata Journal, 13(2), 366–378. https://doi.org/10.1177/1536867X1301300211

2.4.1.2.2 Alteration from baseline in long bone alignment and configuration over 12 months as measured by X-ray analysis.

Using X-ray images of the hip and knees, bone alignment will be evaluated based on the angle formed between the head and neck of the femur and its shaft (Mikulicz angle), the femoral neck-shaft angle (NSA). To ensure consistency, the NSA will be assessed centrally by at least two independent radiologists to ensure consistency across sites. This will be measured according to the standards described in Keats TE Atlas of Roentenographic measurement Mosby 1990 p.289 p.320.

Outcome measures are:

- A. Bone age SD age related zscore (taken from the left wrist x-ray)
- B. Tanner and Whitehouse bone age (TW3)??
- C. Femoral neck-shaft angle (NSA) on left and right legs
- D. Deviation from midline at knee

2.4.1.2.3 Pain perception

Alteration from baseline in pain perception over 12 months is measured by:

- PedsQL Pain Coping Inventory
- PedsQL Pain Questionnaire

PEDSQL Pain Coping Inventory and PEDSQL Pain Questionnaire - to measure pain perception and pain coping strategies. (Varni, J.W., Waldron, S.A., Gragg, R.A., Rapoff, M.A., Bernstein, B.H., Lindsley, C.B., & Newcomb, M.D. (1996). Development of the Waldron/Varni Pediatric Pain Coping Inventory. Pain, 67, 141-150.

https://www.pedsql.org/about_pedsql.html

Separate versions of the PedsQL for completion by the subject (for children aged 5 and over) and for the parent(s)/ legal guardian(s) acting as a proxy for the child are used. When the child is capable of self-completing an age-appropriate version, as assessed by parental and clinician judgement, they will do so. However, if the child is deemed incapable, the proxy version is used alone. It is recommended where possible, the same parent/caregiver should complete the questionnaires at all visits. Thus, two questionnaires, one from the child and one from the parent/guardian, could be available for analysis at each time point.

2.4.1.2.3.1 PedsQL Pediatric Pain Coping Inventory

Composed of 41 questions comprising 5 dimensions:

- 1. Cognitive Self-Instruction
- 2. Problem-Solving
- 3. Distraction
- 4. Seeks Social Support
- 5. Catastrophizing / Helplessness

A 3-point Likert scale from 0 (Never) to 2 (Often) is used to score each question. Total score is calculated as the sum of all question scores divided by the number of questions answered. If more than 50% of the questions in the scale are missing, the score should not be computed. If 50% or more of the questions are completed: the mean of the completed questions is imputed for those that are missing.

Outcome is the total score which will vary between 0 and 2 and will be treated as a continuous variable.

2.4.1.2.3.2 PedsQL Pediatric Pain Questionnaire

The Pediatric Pain Questionnaire is composed of 3 items. Questions on "*how you feel now*" and "worst pain you had this week" scored on a VAS and converted to a score of 0 (no pain) to 100 (Severe pain). The third item refers to the localisation of pain and is not scored.

2.4.1.2.4 PedsQL[™] Generic Core Scales Version 4.0 Short Form (SF15)

Alteration from baseline in HRQOL scores over 12 months as measured by Paediatric Quality of Life Inventory (PedsQL).

Composed of 15 questions comprising 4 dimensions:

- 1. Physical functioning
- 2. Emotional functioning
- 3. Social functioning
- 4. School functioning

A 5-point Likert scale from 0 (Never) to 4 (Almost always) is used to score each question except for the self-reported version completed by young children (ages 5-7) which uses a 3-point scales: 0 (Not at all), 2 (Sometimes) and 4 (A lot). Questions are reversed scored and linearly transformed to a 0-100 scale as follows: 0=100, 1=75, 2=50, 3=25, 4=0.

Score by Dimensions: If more than 50% of the questions in the scale are missing, the scale scores should not be computed. Mean score is calculated as the sum of the question scores divided by the number of questions answered.

Psychosocial Health Summary Score = Sum of the question scores divided by the number of questions answered in the Emotional, Social, and School Functioning Scales.

Physical Health Summary Score = Sum of the question scores divided by the number of questions answered in the Physical Functioning Scale.

If more than 50% of the questions in the scale are missing, the score should not be computed. If 50% or more of the questions are completed: the mean of the completed questions is imputed for those that are missing.

2.5 Study assessments

Baseline observation and *Treatment* visits have a ± 14-day allowable visit window.

Any AEs reported during trial visits, telephone calls or that come to the attention of the trial team by other means, are recorded in the patient's medical notes and the eCRF, within the trial MACRO database.

History of surgical interventions to manage MCDS symptoms are recorded at the screening visit. In addition, any incidence of surgical intervention to manage MCDS-related symptoms during the trial is recorded on the AEs crf.

Blood samples for laboratory safety assessments are taken at each *Baseline observation* visit and 6 monthly during the treatment phase. Bone biochemistry (tests comprise of total calcium and/or adjusted calcium*, 25-OHD [or total Vitamin D, depending on local reporting parameters], Phosphate and PTH) and X-rays are recorded at the same visits

Physical examinations are performed at each visit.

Pain questionnaires (PEDSQL Pain Coping Inventory and PEDSQL Pain Questionnaire) are administered at *Baseline observation* and *Treatment* visits as for AE reporting.

The PedsQL[™] Generic Core Scales Version 4.0 Short Form (SF15) is used to capture participant QoL and is administered at Baseline observation and Dose titration visits.

To aid with study participant retention due to COVID 19, the 12-month visit window can be up to 12 months plus a further 8 weeks.

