**Patients who have planned surgery or planned osteotomy will not automatically be ineligible for the trial. Every potential participant with planned surgery or osteotomy will be assessed clinically on a case by case basis through discussion of the site PI^a, with the CI and/or the clinical members of the TMG during the screening process. NB: Please ensure that patients fulfil the full eligibility criteria prior to enrolling them on to the trial and ensure eligibility is re-assessed after the baseline observation period is complete, and before the participant begins treatment with CBZ. If a patient is deemed unsuitable at the end of the baseline observation period re-assessment time point, further reassessment of eligibility is possible if the Site PI^a and CI are in agreement that the exclusionary results are subject to change. In such cases, eligibility can be re-assessed within a 3 month period. If a patient meets any of the exclusion criteria after the 3 month reassessment period, they will be withdrawn from the study.

Protocol waivers will not be permitted for this trial. Enrolling a patient who does not meet the inclusion/exclusion criteria is considered a protocol waiver and is in breach of Regulation 29 (SI 2004/1031) of the Medicines for Human Use (Clinical Trials) Regulations 2004 and EU Clinical Trial Directive 2001.

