8.7.12 Adverse Events

Participants will be asked at each trial visit and telephone call whether they have experienced any adverse events at times indicated in the schedule of events (Tables 5, 6, 7, 8 & 9). Any adverse events reported during trial visits, telephone calls or that come to the attention of the trial team by other means, will be recorded in the patient's medical notes and the eCRF, within the trial MACRO database. During the trial, participants will be instructed to record any adverse events in their MCDS-Therapy Patient Diary – in either their Baseline, Dose Titration or Stable Dose diary depending on which stage of the trial they are at, for use during trial telephone calls and trial visits. Adverse events will also include recording of any incidence of surgical intervention to manage MCDS-related symptoms.

If a reported adverse event is deemed to be serious, then a Serious Adverse Event form will also need to be completed (see protocol section 10.2 – Recording and reporting of AEs and SAEs) and sent to NCTU (UK only). For international sites sharing of safety information will be defined in the relevant country specific delegation agreement or equivalent.

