4.2 Analysis populations

There will be two analysis populations:

1. Participants who have completed the baseline observation period and have received at least one dose of CBZ.

2. Participants who have completed their baseline observation period and have been prescribed, on average, at least 15 mg/kg of CBZ over their first 12 -months of treatment, i.e. a dose which is at least 75% of the dose recommended from Stage 1. Note that some participants will have longer than 12 months of treatment.

Adverse events will be reported for all participants who start their baseline period.

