4.4.3 Additional secondary analyses

Use of surgical interventions to manage the condition will be captured on the eCRF over the whole follow up period. These will be reported descriptively as the type and proportion of participants experiencing an event per three month period from baseline until the end of trial follow up.

5 Safety

Laboratory safety assessments outside the appropriate local normal reference range will be reported at a participant level. Abnormal physical examinations will be reported at a participant level together with any further details provided.

All AEs occurring from the point of consent to the end of trial participation are recorded in the trial MACRO database eCRF. AEs are assessed for their relationship to treatment and coded as: Unrelated, Unlikely, Possible, Probable, Definitely, or Not assessable. Severity is graded according to the Common Terminology Criteria for Adverse Events (CTCAE), Version 5.0, Published: November 27, 2017.

Grading is based on the following general guideline:

- **Grade 1 Mild**; asymptomatic or mild symptoms; clinical or diagnostic observations only; intervention not indicated.
- **Grade 2 Moderate**; minimal, local, or non-invasive intervention indicated; limiting age-appropriate instrumental Activities of Daily Living (ADL).
- **Grade 3 Severe** or medically significant but not immediately life-threatening; hospitalization or prolongation of hospitalization indicated; disabling; limiting self-care ADL.
- Grade 4 Life-threatening consequences; urgent intervention indicated.
- Grade 5 Death related to AE.

AEs are coded using the Medical Dictionary for Regulatory Activities (MedDRA) version 22.0. The Clinical Data Management System (CDMS) auto-codes the majority of AEs to the latest version of the MedDRA dictionary. If this is not possible, AEs are coded from the MedDRA dictionary by the Cl.

SARs occurring from the first participant's dose of IMP to the last participant's end of follow-up are recorded on the trial MACRO database eCRF. Following this defined active monitoring period for SARs, investigators are still required to report any SARs or SUSARs which are brought to their attention.

For each SAE the following information is collected:

- 1. Full details in medical terms and case description
- 2. Event duration (start and end dates, if applicable)
- 3. Action taken
- 4. Outcome
- 5. Seriousness criteria
- 6. Causality in the opinion of the investigator

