5.1.1 Adverse events

The number of adverse events and adverse reactions (those possibly, probably or definitely related to treatment) and the worst grade AE and AR per participant will be summarised descriptively.

Example table: Number of events per participant

	Mean (SD)	Median (Q1, Q3)	Min, Max
All adverse events			
Adverse reactions (possibly, probably, definitely)			

Example table: Worst grade reported per participant (number, %)

	None	Mild	Moderate	Severe
All adverse events				
Adverse reactions (possibly, probably, definitely)				

The number of participants reporting each type of adverse event (by MedDRA System Organ Class) will be tabulated.

Example table: Number and percentage of participants affected by each adverse event, reported by System Organ Class

Event term		Total		Mild		Moderate		Severe	
	Ν	%	Ν	%	Ν	%	Ν	%	
Blood and lymphatic system disorders									
Cardiac disorders									
Endocrine disorders									
Eye disorders									
Gastrointestinal disorders									
General disorders and administration site conditions									
Immune system disorders									
Infections and infestations									
Injury, poisoning and procedural complications									
Investigations									
Metabolism and nutrition disorders									

The number and percentage of patients experiencing at least one high grade event (grade 3/4/5).

A line listing of all AEs will be reported, by participant, including severity, seriousness and relationship to study treatment.

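### Operations for MCDS are recorded as adverse events, and the SAP's organ-class, grade 3–5 and SAE summaries do not separate them from other harms or by period

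*SAP*

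**What the plan says.** **Recording.** Protocol 8.7.12: "Adverse events will also include recording of any incidence of surgical intervention to manage MCDS-related symptoms". SAP 2.5 says likewise that "any incidence of surgical intervention to manage MCDS-related symptoms during the trial is recorded on the AEs crf".

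**Window and population.** SAP section 5: "All AEs occurring from the point of consent to the end of trial participation are recorded in the trial MACRO database eCRF". SAP 4.2: "Adverse events will be reported for all participants who start their baseline period". Neither place states a split into baseline and treatment periods.

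**Grade and seriousness.** The general guideline for grade 3 in SAP section 5 includes "hospitalization or prolongation of hospitalization indicated". Protocol 10.1 makes inpatient hospitalisation an SAE criterion and exempts no planned or disease-management admission.

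**Summaries.** SAP 5.1.1 counts adverse events and adverse reactions, and says that "the worst grade AE and AR per participant will be summarised descriptively", so these two tables each have an all-events row and a related row. The organ-class table is for all events. A further item reads "The number and percentage of patients experiencing at least one high grade event (grade 3/4/5", again for all events. SAP 5.1.2 counts SAEs and the children with at least one. The AE and SAE listings show relationship to treatment.

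**Surgery elsewhere.** SAP 4.4.3 reports operations descriptively, by type and by three-month period from baseline. SAP 4.3.3.1 has the chief investigator review them for a possible effect on growth. On eligibility, protocol 7.2 says: "Patients who have planned surgery or planned osteotomy will not automatically be ineligible for the trial". SAP 2.2.2 lists planned surgery as an exclusion without that qualification, but SAP 2.2 refers to the protocol for the full criteria.

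**The concern.** An operation to correct a hip or knee deformity is part of the course of MCDS. Once it is on the AE form and involves an admission, it can count in the same way as a serious event of any other kind. The percentage of children with a grade 3–5 event and the number with an SAE are figures that readers lift from a safety section. In a single-arm trial no control group shows how much of either figure is the disease and its management.

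Surgery is foreseeable here. The protocol's background (2.1) names hip and knee deformity as the greatest source of disability, planned osteotomy is not an automatic bar to entry, and the SAP itself prepares a growth model that adjusts for surgery. Because events are collected from consent, an operation during the observation period, before any carbamazepine, enters the same tables.

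What is at stake is how the all-cause figures read. A cluster of operations could make them look worse than the drug's profile warrants, or make a modest number of other serious events harder to see.

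**Working it through.** **1. Trace one operation.** Take an inpatient operation for MCDS that the investigator judges unrelated to carbamazepine and grades 3 under the general guideline.

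| Output | Counts the operation? | Separated within that output? |
|---|---|---|
| Event count, all AEs | Yes | Adverse-reaction row leaves it out |
| Worst grade, all AEs | Yes | Adverse-reaction row leaves it out |
| AEs by organ class | Yes | No |
| Percentage with a grade 3–5 event | Yes | No |
| SAE count and children with an SAE | Yes | No |
| AE and SAE listings | Yes | By hand, from description and relationship |
| SAP 4.4.3 surgery summary | Yes | Operations only |
| Dose-limiting toxicity (protocol 8.8.5) | No: only anaemia, haemolytic anaemia, liver and kidney items qualify | Not applicable |

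The gap is in the third, fourth and fifth rows. That operations stay in these summaries is inferred from the recording rule and the absence of any exclusion; the SAP does not say so in words.

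**2. Time before carbamazepine.** Scheduled baseline time divided by scheduled total time:

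- Stage 2: 6 / (6 + 12) = 33%.
- Stage 1 to 24 months of treatment: 12 / (12 + 24) = 33%, or 18 / (18 + 24) = 43% with the longer baseline.
- Stage 1 with the optional year: 12 / (12 + 36) = 25%, or 18 / (18 + 36) = 33%.

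So 25% to 43% of a completing child's scheduled observation precedes the drug. A child who starts baseline and never takes carbamazepine also counts in the tables.

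**3. Size.** The documents give neither a surgery rate nor an expected adverse event rate, so there is no figure of the plan's to reproduce. The sample size of 40 (11 + 29) was set by feasibility. One thing is exact: a child who has an inpatient operation and no other grade 3–5 event or SAE moves the percentage by 1/40 = 2.5 points.

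For illustration only, let b be the chance that a child has a non-surgical grade 3–5 event (or SAE) and s the chance of an inpatient operation, taken as independent. Then

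share with at least one event = 1 − (1 − b)(1 − s), and the part added by surgery = s(1 − b).

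- b = 5%, s = 10%: 1 − 0.95 × 0.90 = 14.5% (5.8 of 40), against 5.0% (2.0 of 40) without surgery.
- Smallest addition over b = 0–20% and s = 2.5–20%: 0.025 × 0.80 = 2 points (0.8 of 40 children).
- Largest addition over that range: 0.20 × 1.00 = 20 points (8 of 40 children).

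The chance of at least one operated child among 40 is 1 − (1 − s)^40: 0.64 at s = 2.5% and 0.99 at s = 10%. On these assumptions the question is likely to arise even if surgery is uncommon.

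**The case against.** The strongest reply is that all-cause reporting is deliberate and conservative. Protocol 10.1 defines an adverse event without regard to cause, so an all-cause percentage does not claim to measure toxicity. The SAP codes relationship for every event, gives adverse reactions their own row for counts and worst grade, and lists every AE and SAE. With at most 40 children, and with SAP 4.4.3 giving operations by type and period, a reader of the full report can remove them by hand. Planned surgery is screened case by case, and eligibility is re-checked before treatment, so operations may be few. The stage 2 dose has already been agreed, and no decision rule uses the grade 3–5 percentage.

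Most of this stands, and it rules out several stronger readings that a reader might infer:

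- That the plan overstates carbamazepine's toxicity by some multiple. Only the all-cause figures are affected, and any multiple would rest wholly on assumed rates.
- That operations cannot be separated at all. They can, from the listings, but not from the organ-class, grade 3–5 or SAE summaries.
- That operations are double counted. They are reported in two places, but no statistic adds the two, and SAP 4.4.3 is a descriptive additional analysis rather than an outcome listed in SAP 2.4.1.2.
- That surgery should leave the main safety rows. An operation for worsening deformity could itself be a harm: SAP 4.3.3.2 allows for secondary effects on bone health. Exclusion would depend on unblinded causality judgement, and the SAP is dated 8 February 2024, after the last permitted visit of 31 January 2024.

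What the reply does not meet is that three summary outputs lack even the related row that the other two have, and that no AE table is said to distinguish events before treatment from events on it.

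**Conclusion.** The point holds as a gap in presentation. As written, the organ-class table, the grade 3–5 percentage and the SAE counts pool disease-management surgery, before and during treatment, with all other harms. The adverse-reaction rows are unaffected provided that surgery is judged unrelated. The primary growth analysis is outside this point.

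The size cannot be known from the documents. The firm figure is 2.5 percentage points per operated child with no other such event, taking the planned 40 children as denominator. The 2 to 20 point range rests on the assumed rates and on independence. The argument also assumes that inpatient operations are graded by the general hospitalisation wording; an operation without admission need not reach grade 3 or become an SAE. The change is worth making because it is cheap and these are the safety figures most likely to be quoted.

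**What to change.** In SAP 5.1.1 and 5.1.2:

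1. Keep the all-cause AE (including organ class), worst-grade, grade 3–5 and SAE summaries as the main rows.
2. Add a supplementary row to each that excludes operations to manage MCDS, using the operations already identified for SAP 4.4.3. Complications of surgery, and any operation judged related to carbamazepine, stay in.
3. Add related-only rows to the grade 3–5 and SAE summaries, with the same definition of adverse reaction as the count and worst-grade tables.
4. State for each operation whether it fell in the baseline or the treatment period.

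No new data are needed, and individual and expedited safety reporting are unchanged. The cost is one or two extra rows per table. Because the SAP postdates the last permitted visit, the added rows should be labelled supplementary.
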